## **17.5 Monitoring**

### **17.5.1 Study Monitoring**

The study chair and faculty statistician will review the trial data every 3 months to identify accrual, toxicity, and endpoint problems that might be developing. The faculty statistician will prepare a report containing accrual, adverse events, and efficacy data which will be submitted to the MCCC Data and Safety Monitoring Board (DSMB) on a semi-annual basis.

### **17.5.2 Safety Stopping Rule**

Pre-Amendment 3: Safety stopping rules will be applied to each treatment arm separately. If 3 or more of the first 10 patients randomized to a given treatment arm or 30% of more of patients randomized to that treatment arm thereafter develops a grade 4 hematologic or non-hematologic toxicity possibly, probably or definitely related to treatment, the enrollment to the trial will be temporarily suspended so that all AE data can be examined. The study chair and the faculty statistician will formulate a trial recommendation to present to the IRB for approval. These instances will also be reported to the MCCC DSMB.

Post-Amendment 3: This safety stopping rule will be applied to each treatment arm separately for the patients enrolled after the activation of Amendment 3. If 2 or more of the first 6 patients randomized to a given treatment arm or 30% of more of patients randomized to that treatment arm thereafter develops a Grade 4 hematologic or non-hematologic toxicity possibly, probably or definitely related to treatment, the enrollment to the trial will be temporarily suspended so that all AE data can be examined. The study chair and the faculty statistician will formulate a trial recommendation to present to the IRB for approval. These instances will also be reported to the MCCC DSMB.

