### 3.8 Study Safety Assessment

The safety stopping boundary was crossed after 12 patients had received at least one cycle of treatment, with 5 of these 12 patients developing a Grade 4 toxicity or dying on treatment. The study was temporarily closed to accrual on 02Apr2018 for the protocol chair and the study biostatistician to review all the AE data.

The findings are summarized below:

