- Common ( $\geq 1\%$  and  $< 10\%$ ): lymphopenia, pancytopenia, dyspepsia, mucosal inflammation, URTI, UTI, pneumonia, oral candidiasis, sepsis (including fatal sepsis), cellulitis, oral herpes, sinusitis, nasopharyngitis, bronchitis, herpes zoster, influenza, conjunctivitis, esophagitis, skin infection, fungal skin infection, oral fungal infection, septic shock, increased AST, increased ALT, increased blood bilirubin, increased alkaline phosphatase, increased GGT, gait disturbance, confusional state, rash, pruritic rash, macular rash, maculo-papular rash, dermatitis acneiform, palmar-plantar erythrodysesthesia syndrome
- Uncommon ( $\geq 0.1\%$  and  $< 1\%$ ): sedation, dermatitis bullous

Reproductive toxicology studies have not been conducted with alisertib. Given the outcomes associated with Aurora A kinase inhibition and the effects of alisertib observed in reproductive tissues in repeat-dose toxicology studies, it is anticipated that alisertib could be a reproductive and developmental toxicant.

Because alisertib may cause anemia, neutropenia, leukopenia, lymphopenia, and thrombocytopenia, patients on alisertib may experience the anticipated sequelae of infection, hemorrhage, or bleeding.

Because of the effects of alisertib on the gastrointestinal mucosa, there is a potential risk of mucosal bleeding, GI bleeding, and the associated infections and sepsis.

Cases of cardiac abnormalities have been infrequently observed in patients receiving treatment with alisertib, including decreased left ventricular ejection fraction, tachycardia, and 1 case of QT prolongation. The causal relationship between cardiac dysfunction and alisertib has been confounded by patients' prior history of other cardiac abnormalities.

Alisertib is structurally related to the benzodiazepines and may cause somnolence, confusion, dizziness or gait disturbance associated with the onset of maximal plasma concentration (about 3 hrs post-dose). For this reason, patients should not drive, operate dangerous machinery, or perform any other task requiring full alertness and/or coordination if these effects are experienced while enrolled on study. Sedative effects have been managed by administration of divided doses and dose administration at bedtime, although dose reductions have sometimes been required.

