**13. ADVERSE EVENT REPORTING REQUIREMENTS**

The site principal investigator is responsible for reporting any/all serious adverse events to the sponsor as described within the protocol, regardless of attribution to study agent or treatment procedure.

The sponsor/sponsor-investigator is responsible for notifying FDA and all participating investigators in a written safety report of any of the following:

- Any suspected adverse reaction that is both serious and unexpected.
- Any findings from laboratory animal or *in vitro* testing that suggest a significant risk for human subjects, including reports of mutagenicity, teratogenicity, or carcinogenicity.
- Any findings from epidemiological studies, pooled analysis of multiple studies, or clinical studies, whether or not conducted under an IND and whether or not conducted by the sponsor, that suggest a significant risk in humans exposed to the drug.
- Any clinically important increase in the rate of a serious suspected adverse reaction over the rate stated in the protocol or Investigator’s Brochure (IB).

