### 13.5 Required Routine Reporting

Pretreatment symptoms/conditions to be graded at baseline and adverse events to be graded at each evaluation per CTCAE v4.0 grading **unless** otherwise stated in the table below:

CTCAE System Organ Class (SOC)	Adverse event/Symptoms	Baseline	Each evaluation
Blood and Lymphatic System Disorders	Anemia	X	X
Gastrointestinal Disorders	# of stools	X	
	Diarrhea		X
	Nausea	X	X
	Vomiting	X	X
	Mucositis Oral	X	X
General disorders and administration site conditions	Fatigue	X	X
	Injection site reaction		X
Investigations	Platelet Count Decreased	X	X
	Neutrophil Count Decreased	X	X
	White Blood Cell Decreased	X	X

CTCAE System Organ Class (SOC)	Adverse event/Symptoms	Baseline	Each evaluation
Metabolism and nutrition disorders	Anorexia	X	X
Renal and urinary disorders	Acute Kidney Injury	X	X
Skin and subcutaneous tissues	Rash acneiform	X	X
	Rash maculo-papular	X	X

**13.5.1 Submit via appropriate MCCC Case Report Forms (i.e., paper or electronic, as applicable) the following AEs experienced by a patient and not specified in Section 13.5:**

13.5.1.1 Grade 2 AEs deemed *possibly, probably, or definitely* related to the study treatment or procedure.

13.5.1.2 Grade 3 and 4 AEs regardless of attribution to the study treatment or procedure.

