13.5.1.3 Grade 5 AEs (Deaths)

13.5.1.3.1 Any death within 30 days of the patient's last study treatment or procedure regardless of attribution to the study treatment or procedure.

13.5.1.3.2 Any death more than 30 days after the patient's last study treatment or procedure that is felt to be at least possibly treatment related must also be submitted as a Grade 5 AE, with a CTCAE type and attribution assigned.

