## 17.2 Sample Size/ Accrual Rate

Melichar et al reported the results of a Phase II clinical trial of alisertib (administered at 50 mg BID for 7 days of a 21 day cycle) monotherapy in women with chemo-resistant metastatic breast cancer. The response rate among the 14 women with triple negative breast cancer was 7.1 % (median PFS: 1.5 months). The response rate among the 26 women with hormone receptor positive disease was 23.1% (median PFS: 7.9 months). Given these results and the expectation that approximately 10% of the patients who will be enrolled onto this trial will have triple negative breast cancer, we anticipate the response rate with alisertib alone will be 20%.

A randomized phase II clinical trial design (proposed by Jung et al) which incorporates a prospective control treatment and a futility stopping rule was chosen to assess whether the tumor response rate with the addition of fulvestrant to alisertib will be greater than that of alisertib alone by at least 20%, when the tumor response rate for alisertib alone is assumed to be 20%. The randomized phase II clinical trial design with a prospective control group proposed by Jung takes into account the interim analysis for futility so that overall design parameters are met.

With a sample size of 45 patients per arm, a one sided alpha=0.15 sequential binomial test of the difference in two independent proportions will have a 85% chance of detecting that the response rate with the addition of fulvestrant to alisertib is at least 20% or greater

than the response rate with alisertib alone, when the true response rate for alisertib alone is 20% or less. The null hypothesis that the difference in tumor responses is less than 20% would be rejected if at least 4 more tumor responses are seen with the combination of fulvestrant and alisertib than with alisertib alone.

It is anticipated that none of the patients who are pre-registered will fail to obtain an ER result from the biopsy of a metastatic lesion. However, some patient may cancel participation prior to registration/randomization or after randomization but prior to the start of assigned treatment and other patients may be found to be ineligible. These patients will be replaced. It is anticipated that an additional 6 patients may be enrolled to account for these situations.

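### The safety stopping rule in Section 17.5.2 counts related Grade 4 toxicity only, so a treatment-related death recorded only as Grade 5 does not move the trial's one numerical safety boundary

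*Combined protocol and SAP*

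**What the plan says.** Section 17.5.2 has two paragraphs, one for patients enrolled before Amendment 3 and one for those enrolled after its activation. Both apply to each arm separately and define the counted event in the same words apart from a capital letter: a patient counts if she "develops a grade 4 hematologic or non-hematologic toxicity possibly, probably or definitely related to treatment". The earlier limit was 3 of the first 10 patients on an arm. The current limit is 2 of the first 6. Both then continue at 30% of the arm. Crossing suspends enrolment to the whole trial temporarily so that the adverse event data can be reviewed.

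Section 13.5.1 keeps deaths in a category of their own. One item covers "Grade 3 and 4 AEs regardless of attribution to the study treatment or procedure". The next covers Grade 5, and adds that a later death (beyond 30 days from the last treatment) that may be "treatment related must also be submitted as a Grade 5 AE, with a CTCAE type and attribution assigned".

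Section 3.8 reports that the boundary was crossed after 12 patients had received at least one cycle, with "5 of these 12 patients developing a Grade 4 toxicity or dying on treatment", and that accrual was closed temporarily. The summary that follows is not in the text available for review.

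**The concern.** A safety boundary should give the worst related outcome at least the weight of a lesser one. As worded, a related Grade 4 neutropenia counts, while a related death with no related Grade 4 event on record does not. Such a death is foreseeable: Section 8.1.7 lists sepsis, fatal cases included, among alisertib's common toxicities.

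Where the protocol means Grade 5 elsewhere, it says so. Section 13.3.2 names Grades 4 and 5 together, and the table in Section 13.3.4 covers Grades 3 to 5. It is therefore unsafe to read Grade 4 in Section 17.5.2 as Grade 4 or worse.

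This is the only numerical safety trigger for patients enrolled after Amendment 3, in a trial that had already paused once on safety grounds. The wording also leaves open whether Sections 3.8 and 17.5.2 count the same events.

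**Working it through.** **The plan's own figure.** No operating characteristics are stated for the rule, so there are none to reproduce. The only worked use is the 5 of 12 in Section 3.8. The arm split and the attribution of those events are not available, so I assume splits from 4:8 to 8:4 and that all five events were at least possibly related.

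- If all five count, one arm must have at least 3 events, and the limit of 3 in the first 10 is crossed under every split.
- If one or two were deaths recorded only as Grade 5 and are not counted, 4 or 3 events remain. These can divide 2:2 or 2:1, so crossing is no longer certain.
- If three or more were such deaths, at most 2 events remain and the limit cannot be reached.

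The description in Section 3.8 and the wording of Section 17.5.2 can therefore give different answers on the same data.

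**Inputs.** The limits (2 of the first 6, then 30%) are from Section 17.5.2. The arm size is from Section 17.2: "With a sample size of 45 patients per arm". The post-Amendment 3 rule covers only patients enrolled after its activation. That number is not in the available text, so 45 is an upper limit and I also show an assumed 30. All event rates are assumed. Let a be the proportion with a related Grade 4 event and b the further proportion with a related Grade 5 event and no related Grade 4 event. The counted proportion p is a as written, and a + b with deaths included.

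**First-6 look.** P(X ≥ 2) = 1 − (1 − p)^6 − 6p(1 − p)^5. For example:

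- p = 0.10: 1 − 0.5314 − 0.3543 = 0.114
- p = 0.15: 1 − 0.3771 − 0.3993 = 0.224

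**Whole rule.** This is an exact recursion over patients. It stops at 2 events within the first 6, or when X/n ≥ 0.30 after any later patient n. The text does not say how often the 30% limit is checked; I read it as a check after each patient.

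**Either arm.** Crossing on one arm suspends the whole trial. With independent arms and equal rates, P(at least one pause) = 1 − (1 − P)².

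Each cell gives the value as written → the value with related Grade 5 counted:

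| Assumed a + b | First 6, per arm | Whole rule, 30 per arm | Whole rule, 45 per arm | Either arm, 45 per arm |
|---|---|---|---|---|
| 10% + 2% | 0.114 → 0.156 | 0.142 → 0.200 | 0.142 → 0.200 | 0.264 → 0.361 |
| 10% + 5% | 0.114 → 0.224 | 0.142 → 0.301 | 0.142 → 0.303 | 0.264 → 0.514 |
| 20% + 5% | 0.345 → 0.466 | 0.491 → 0.677 | 0.500 → 0.699 | 0.750 → 0.909 |

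**A smaller assumption.** With 10% + 1%, the whole rule over 45 patients moves from 0.142 to 0.170.

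**The starkest case.** The chance of two or more Grade 5-only deaths among the first 6 is 0.006 if b = 2% and 0.033 if b = 5%. It is unlikely at these rates, but when it happens the count is 0.

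**The case against.** The best counter-argument is that the gap may exist only on paper. Section 3.8 is the sole account of the boundary in use, and it puts deaths beside Grade 4 events. The missing text after it might say how deaths were counted. The rule also asks whether a patient develops a Grade 4 toxicity, not whether Grade 4 was her worst grade. A fatal toxicity often passes through a life-threatening stage, and blood counts are taken regularly, so some patients with fatal sepsis would already count through a recorded related Grade 4 neutropenia.

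Deaths are also watched in other ways:

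- Section 13 requires the sponsor to notify the FDA and investigators of "Any clinically important increase in the rate of a serious suspected adverse reaction".
- Section 13.3.4 requires immediate reporting of serious events, and Section 13.4.2 requires 24-hour reporting of deaths within 30 days of the last dose.
- Section 17.2 names toxicity among the considerations that might lead to early closure.
- Section 17.5.1 sets three-monthly review and semi-annual reports to the DSMB.

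Much of this stands. It limits the gap to related deaths with no recorded related Grade 4 event, and it means such deaths would not go unnoticed. The size also depends wholly on assumed rates. But none of these provisions puts a death into the count, and past practice described in a background section does not define the operative rule. If the team already counts deaths, the correction only records what it does.

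**Conclusion.** The point holds on the available text. The post-Amendment 3 rule as written gives no weight to a related death recorded only as Grade 5, and Section 3.8 suggests a different count. Under the three tabulated cases, leaving such deaths out lowers the chance of a pause per arm by about 4 to 12 percentage points at the first-6 look. Over 45 patients per arm, with a check after each patient, it lowers it by about 6 to 20 points (6 to 19 for 30 per arm). These sizes rest on assumed rates and on that reading of the 30% limit; the effect shrinks towards zero as Grade 5-only deaths become rarer. That such deaths score zero rests on the wording alone. This should be fixed. It is a cheap improvement to a safety trigger and does not bear on the efficacy design.

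**What to change.** In the post-Amendment 3 paragraph of Section 17.5.2, insert *or Grade 5* after *Grade 4*, and leave the attribution clause and the limits as they are. The attribution clause still leaves out deaths judged unrelated, including deaths from progressive disease, which Section 13.4.2 has reported as Grade 5. Section 3.8 needs no edit.

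The cost is one phrase and more frequent temporary pauses. In the tabulated cases the per-arm chance of a pause rises by the amounts given in the verdict. With equal rates in both arms and 45 patients per arm, the chance of at least one pause rises from 0.26 to 0.36, from 0.26 to 0.51 and from 0.75 to 0.91, or about 10, 25 and 16 points. If deaths are already counted in practice, the real increase is smaller or nil. Sample size and the primary analysis are unaffected.

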### 12.1 Definitions

Evaluable for toxicity: All patients will be evaluable for toxicity from the time of their first treatment with alisertib.

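### The safety boundary in Section 17.5.2 counts patients randomized, so patients who are never treated dilute the 30% part and can use up a first-six place

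*Combined protocol and SAP*

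**What the plan says.** The rule in force since Amendment 3 (Section 17.5.2) applies to each arm separately and has two parts, a fixed count and a running percentage: "If 2 or more of the first 6 patients randomized to a given treatment arm or 30% of more of patients randomized" to the arm after that. The qualifying event is a Grade 4 toxicity at least possibly related to treatment. When either part is met, "the enrollment to the trial will be temporarily suspended so that all AE data can be examined". The rule before Amendment 3 used the same base: "If 3 or more of the first 10 patients randomized to a given treatment arm".

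Three other places bear on who is counted:

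- Section 17.2 foresees patients who cancel "after randomization but prior to the start of assigned treatment". It replaces them and allows 6 extra patients for this and related losses. Section 6.4.8 gives defined routes to it: withdrawal of consent before treatment, or liver values on Cycle 1 Day 1 that bar the start of treatment.
- Section 12.1 defines the toxicity-evaluable set: "All patients will be evaluable for toxicity from the time of their first treatment with alisertib".
- Section 3.8 reports the earlier crossing on a treated basis: "The safety stopping boundary was crossed after 12 patients had received at least one cycle of treatment, with 5 of these 12 patients" having a Grade 4 toxicity or dying on treatment.

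Section 17.5.2 does not say that a patient who cancels before treatment leaves the safety count.

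**The concern.** A treatment-related Grade 4 toxicity requires treatment. A randomized patient who never starts can add to the denominator but never to the numerator. In the 30% part, that dilution is permanent. In the count part, such a patient can take one of the six places, so that two events must come from five patients.

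This is the trial's only numerical safety boundary, and it was revised after 5 of 12 patients had a Grade 4 toxicity or died on treatment. Its sensitivity should not depend on how many patients drop out before the first dose. The base in Section 17.5.2 also disagrees with Section 12.1 and with the way Section 3.8 reports the crossing. As written, two people applying the rule to the same data could reach different answers.

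**Working it through.** **The plan's own figure.** Section 3.8 gives 5 of 12. 5/12 = 41.7%, above 30%; since 0.30 × 12 = 3.6, 4 of 12 would have been enough. Five events would still reach 30% with up to 16 in the denominator (5/16 = 31.3%, 5/17 = 29.4%). The reported crossing is consistent with a 30% mark but does not show which base was used. Section 17.5.2 states no operating characteristics to reproduce.

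**Share never treated.** Section 17.2 plans 45 per arm (90) plus 6, which is the 96 of Section 17.6. 6/96 = 6.25%. This is an upper bound, because the 6 also cover cancellations before randomization and ineligible patients, some of whom may be treated (Section 6.4.6).

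**30% part at full size.** If all 6 were randomized and never treated, 30% of randomized equals 0.30 × 96/90 = 32% of treated. Per arm, 0.30 × 48 = 14.4, so 15 events are needed; on 45 treated, 0.30 × 45 = 13.5, so 14. The difference is one event per arm.

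**First-six part.** P(2 or more of n) = 1 − (1−p)^n − n·p·(1−p)^(n−1).

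- p = 0.30, n = 6: 1 − 0.1176 − 0.3025 = 0.58. n = 5: 1 − 0.1681 − 0.3602 = 0.47.
- p = 0.40, n = 6: 1 − 0.0467 − 0.1866 = 0.77. n = 5: 1 − 0.0778 − 0.2592 = 0.66.

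At the upper-bound share, the chance that at least one of the six never starts is 1 − (90/96)^6 = 0.32.

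**Whole rule, by simulation.** The following are assumptions, not in the documents: accrual of 0.5 to 4 patients per arm per month; 42 patients per arm after Amendment 3; 6.25% never treated; Grade 4 onset uniform over Cycle 1; continuous checking; a cumulative denominator. There were 1,200 runs per setting, with both bases applied to the same simulated patients. Events count when they occur.

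| True rate | Accrual per arm per month | Fires, randomized base | Fires, treated base | Mean randomized at firing (randomized / treated base) |
|---|---|---|---|---|
| 20% | 1 | 0.44 | 0.49 | 7.6 / 8.3 |
| 20% | 4 | 0.39 | 0.45 | 8.7 / 9.6 |
| 30% | 1 | 0.79 | 0.84 | 9.0 / 9.1 |
| 30% | 4 | 0.74 | 0.80 | 10.6 / 10.7 |
| 40% | 1 | 0.95 | 0.97 | 7.7 / 7.4 |
| 40% | 4 | 0.94 | 0.97 | 9.8 / 9.5 |

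A second simulation that also counted events when they occur gave 0.78 to 0.81 against 0.82 to 0.85 at a true 30% rate, and at most about 2 points at 40%. Together these put the loss at about 4 to 6 points at 30% and 1 to 3 points at 40%. At 50% the rule fires almost always on either base.

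**Patients still in Cycle 1.** With no never-treated patients, the full rule at a true 30% rate fires 0.848 on the randomized base against 0.852 on a Cycle 1 completed base at 0.5 per arm per month, and 0.802 against 0.845 at 4. The effect is small unless accrual is fast, and it is temporary because later events still count.

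**The case against.** The strongest reply is that this is a wording mismatch with little practical effect. Section 3.8 reports the earlier crossing in patients with at least one cycle, although the rule then also said randomized. That suggests the team already counts treated patients. It does not prove it: Section 3.8 includes deaths on treatment, which the rule does not name, and the available text gives no split by arm. If the team does count treated patients, the written boundary is not the one being run, which is also a reason to correct it.

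The rule triggers a temporary pause, not a test with stated error rates. Section 17.5.1 adds toxicity review every 3 months and semi-annual reports to the monitoring board, and Section 17.2 allows early closure for toxicity. These are real safeguards and they limit the consequence.

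A reader might infer three stronger claims, which the documents do not support:

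- *The rule fires later.* Among arms that fire, mean enrollment differs by 0.3 patients or less in the table at true rates of 30% and 40%.
- *Patients still in Cycle 1 cannot contribute and should be left out.* The rule counts an event once it develops and sets no cycle window, and Section 11 schedules hematology on Cycle 1 Day 15. These patients cannot dilute the two-of-six count at all. For the 30% part alone, at a true rate of 40% and 4 per arm per month, a Cycle 1 completed base fires at 14.0 patients on average against 12.7 for the randomized base.
- *The rule fires less often than the toxicity rate warrants.* Checked continuously as written, it already fires in about 39% to 44% of arms at a true rate of 20%, below its own 30% mark.

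**Conclusion.** The point holds for patients who are never treated. Section 17.5.2 keeps them in both parts of the boundary, against Sections 12.1 and 3.8, and they can only make the rule less sensitive. The effect is clearest in the first six: one non-starter costs about 11 points at a true 30% rate (0.58 to 0.47) and 10 to 11 points at 40% (0.77 to 0.66). Over the whole rule the loss is modest: about 4 to 6 points at 30% and 1 to 3 points at 40%, with enrollment at firing essentially unchanged.

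The whole-rule figures rest on the upper-bound 6.25% never treated and on assumed accrual, event timing and continuous checking, none of which the documents state. With fewer non-starters the loss shrinks toward zero. The first-six probabilities need only the binomial and one non-starter. The reason to act is that the sections disagree on who is counted and the correction is simple, not that the present rule is ineffective.

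**What to change.** In Section 17.5.2, replace *patients randomized to* the arm with *patients who started treatment on* the arm, in both parts of the post-Amendment 3 rule. State that the first six are taken in order of first dose. Leave the thresholds as they are. This brings the rule into line with Section 12.1 and onto a treated basis, as in Section 3.8.

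Do not add a condition that patients must have completed Cycle 1 or already had a qualifying event. That would admit patients still in Cycle 1 only if they had an event, and would drop treated patients who stop early without one. At a true 20% rate and 4 patients per arm per month, it raises firing from about 0.38 to 0.56.

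The cost is one phrase in an amendment and slightly more temporary suspensions at lower true rates: about 5 to 6 points at 20% under the upper-bound assumption (0.44 to 0.49 at 1 per arm per month, 0.39 to 0.45 at 4).
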